5.8 Subject Discontinuation

An intent to treat approach will be used. All data acquired prior to termination for the reasons outlined below will be included in the primary analysis unless patient withdraws consent. Every effort will be made to conduct a final study visit with the participant and participants will be followed clinically until, if applicable, all adverse events resolve.

- Withdrawal of consent.
- Withdrawal by the participant.
- Withdrawal by the investigator.
- Intercurrent illness or event that precludes further visits to the study site or ability to evaluate disease (e.g.-mental status change, large pleural effusion).
- Grade 4 or higher adverse events as defined by the CTCAE or life threatening AEs not covered by the CTCAE of the same preferred term related to the study medication, excluding conditions present at baseline or those directly related to skeletal complications of Osteogenesis Imperfecta.
- Clinically significant allergy or hypersensitivity to fresolimumab.
- Pregnancy.
- QTc interval of > 500msec.
- Clinically significant oral or mucosal bleeding with resulting hemoglobin of < 8g/dL.
- Development of keratoacanthoma, squamous cell or basal cell carcinoma.
- Development of any cancer.

5.9 Data Quality and Monitoring Measures

As much as possible data quality is assessed at the data entry point using intelligent on-line data entry via visual basic designed screen forms. Data element constraints, whether independent range or format limitations or 'relative' referential integrity limitations, can be enforced by all methods employed for data input. QA reports assess data quality post-data entry. As we note, data quality begins with the design of the data collection forms and procedures and incorporates reasonable checks to minimize transcription and omission errors. Of the more important quality assurance measures are the internal validity checks for reasonableness and consistency.

- Data Monitoring: The RDCRN DMCC identifies missing or unclear data and generates a data query to the consortium administrator contact.
- Data Delinquency Tracking: The Data Management and Coordinating Center will monitor data delinquency on an ongoing basis.

5.10 Quality Control: Study Related Procedures

Accurate, consistent and reliable data will be ensured through the use of standard practices and procedures. The DMCC will audit the Investigators' source data against eCRF entries and verify that the data are accurate.

6. Statistical Considerations

This study is designed to assess the safety and tolerability of fresolimumab in patients with Osteogenesis Imperfecta.

Sample Size: No formal sample size calculations were done for this study. The sample size was selected to allow for an initial assessment of safety in this population and dose range and feasibility of enrollment in this rare disorder. The sample size is 8 for the single dose study and 8 for the repeat dose study. The overall enrollment will be 16.

If needed, 2 additional patients will be enrolled in the repeat dose study to account for a drop-out rate of 20%.

Treatment-Related Adverse Events will be summarized by dose groups. Changes in vital signs, EKG, shifts in laboratory assessments and physical examinations, and patient-reported symptoms will be described. These will assess the primary endpoint of safety. Percent change in bone remodeling markers will be analyzed using a mixed model. BMD in the lumbar spine and the hip at 6 months for single dose study and 12 months for the multiple dose study will be compared to pretreatment levels using a Wilcoxon Signed Rank test. Percent change in the variables of the pulmonary function tests, and change in the 6-minute walk tests, and Numeric Rating Scale (NRS) for pain will be evaluated by Wilcoxon Signed Rank test. Values for derived pharmacokinetic variables, including Cmax, area under the curve, distribution, half-life (T1/2a), elimination half-life (T1/2b), clearance (CL), and volume of distribution at steady state (Vss), will be calculated as previously described and summarized by dose-group using descriptive statistics.

7. Data Management

The results from Screening and data collected during the study will be recorded in the

patient's CRF (either paper or electronic CRF). To maintain confidentiality, the patients will be identified only by numbers or initials. All source documents, records, and reports will be retained by the study site in accordance with 21 CFR 312.62(c). All primary data, or copies thereof (e.g., laboratory records, CRFs, data sheets, correspondence, photographs, and computer records), which are a result of the original observations and activities of the study and are necessary for the reconstruction and evaluation of any study report, will be retained in the study site archives.

All study data will be collected via systems created in collaboration with the RDCRN Data Management and Coordinating Center and will comply with all applicable guidelines regarding patient confidentiality and data integrity. Biological samples collected for safety testing will be shipped to a CLIA certified laboratory for analysis. Biological samples collected for pharmacokinetics and drug efficacy will be shipped to Genzyme/Sanofi for analysis.

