Primary Outcome Measures:	
Single dose study (Stage 1):
 
 1) Pharmacokinetics of fresolimumab with single dose administration 2) To evaluate the safety of single administration of fresolimumab in adults with moderate-to-severe OI with respect to: 
 • Vital signs • Laboratory variables • EKG (Corrected QT interval) • Adverse events and serious adverse events 
Repeat dose study (Stage 2):
 
To evaluate the safety of repeat dose administrations of fresolimumab in adults with moderate-to-severe OI with respect to:
 
 • Vital signs • Laboratory variables • EKG • Adverse events and serious adverse events

Secondary Outcome Measures:	
Single dose study (Stage 1): Effect of fresolimumab with respect to:
 
 • Markers of bone turnover in blood (type 1 procollagen, N-terminal or P1NP, Osteocalcin or Ocn, and C-terminal telopeptide or CTX) • Areal bone mineral density (aBMD) at the hip or the lumbar spine as measured by dual-energy X-ray absorptiometry (DXA) scan 
Repeat dose study (Stage 2): Effect of fresolimumab with respect to:
 
 • Markers of bone turnover in blood (type 1 procollagen, N-terminal or P1NP, Osteocalcin or Ocn, and C-terminal telopeptide or CTX) • Areal bone mineral density (aBMD) at the hip or the lumbar spine as measured by dual-energy X-ray absorptiometry (DXA) scan • Bone density and estimated strength by pQCT of forearm • Pain score as assessed by Numeric Rating Scale (NRS) • Forced expiratory volume in 1 second (FEV1), forced vital capacity (FVC) as measured by pulmonary function tests • QOL as assessed by PROMIS® • Functional capacity as assessed by the 6-minute walk test.

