Statistical Considerations (sample size and analysis plan):	
This study is designed to assess the safety and tolerability of fresolimumab in patients with Osteogenesis Imperfecta.
 
Sample Size: No formal sample size calculations will be done for this study. The sample size was selected to allow for an initial assessment of safety in this population, dose range and feasibility of enrollment in this rare disorder. The sample size is 8 for the single dose study and 8 for the repeat dose study. Participants enrolled in Stage 1 of this study may be enrolled in Stage 2 of the study if they meet eligibility. The overall enrollment will be 16. If needed, 2 additional patients will be enrolled in the repeat dose study to account for a dropout rate of 20%.
 
Treatment-Related Adverse Events will be summarized by dose groups. Changes in Vital signs (heart rate, blood pressure, respiratory rate, and body temperature), EKG, changes in laboratory assessments and physical examination findings, and patient-reported symptoms will be described. These variables will assess the primary endpoint of safety. Percent change in bone remodeling markers will be analyzed using a mixed model. BMD in the lumbar spine and the hip at 6 months for the single dose study and at 12 months for the multiple dose study will be compared to pretreatment levels using a Wilcoxon Signed Rank test. Percent change in the variables of the pulmonary function tests, and changes in the 6-minute walk test and the Numeric Rating Scale (NRS) for pain will be evaluated by Wilcoxon Signed Rank test. Values for derived pharmacokinetic variables, including Cmax, area under the curve, distribution, half-life (T1/2a), elimination half-life (T1/2b), clearance (CL), and volume of distribution at steady state (Vss), will be calculated as previously described and summarized by dose-group using descriptive statistics.

Sponsors (federal, state, foundation and industry support):	National Institutes of Health (NIH), The Osteogenesis Imperfecta Foundation (OIF), Genzyme

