Aim 2. Evaluate the safety of repeated dose administration of fresolimumab in adult patients with moderate-to-severe OI (Stage 2). This will also be a multicenter wherein fresolimumab will be administered every three months (group 1) or every six months (group 2) for a total treatment period of 12 months (n=4 patients per group). The dose to be administered (1 or 4 mg/kg) will be chosen after completion of Stage 1. The primary Stage 2 endpoint will be safety measures assessed over 12 months. The secondary endpoints will be changes in markers of bone remodeling, bone mineral density, estimated strength as assessed by peripheral QCT of the forearm, pulmonary function tests, pain as assessed by NRS, QOL as assessed by the PROMIS questionnaire, and changes in the 6-minute walk test.

3. Background

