3.5 Fresolimumab for inhibition of TGF β in humans

The safety of fresolimumab has been evaluated by Genzyme in non-clinical studies using rodent and non-human primate models. Fresolimumab has also been used in humans with idiopathic pulmonary fibrosis, idiopathic focal segmental glomerulosclerosis¹⁸, advanced renal cell carcinoma and malignant melanoma¹⁹ in Genzyme-sponsored clinical studies. The nonclinical and clinical data gathered to date support single- and repeat-dose administration of fresolimumab in humans.

The effects of fresolimumab on bone turnover and bone mass have not been studied, and the sponsor wishes to conduct a phase I study of fresolimumab in a Mendelian skeletal condition with proven over-activity of TGF β . This would be the first disease-specific therapy to be investigated in humans with OI.

[figure not shown]
4. Study Design and Methods

This is a multicenter, phase I study to evaluate the safety of single and repeat dose administration of fresolimumab in adult patients with moderate-to-severe OI. Stage 1 will involve a single dose of fresolimumab wherein those in group 1 will be administered a dose of 1 mg/kg body weight and those in group 2 will be administered a dose of 4 mg/kg body weight; there will be no randomization in this stage. Stage 2 will involve repeat doses of fresolimumab; in this stage, the Data Management Coordinating Center will randomize patients into two groups – individuals in group 1 will receive 4 doses of fresolimumab at months 0, 3, 6, and 9 and individuals in group 2 will receive two doses of fresolimumab at months 0 and 6.

Design

After the four individuals complete the 1 mg/kg dose (group 1, stage 1), an independent Data Safety and Monitoring Board appointed by the National Institute of Health will review the safety data. The decision to proceed with the 4 mg/kg single dose administration (group 2, stage 1) will be determined by the DSMB based on adverse events, safety data collected, and discontinuation criteria outlined in sections 5.6 and 5.7 of the protocol.

If the study proceeds, the study procedures for the 4 mg/kg (group 2, stage 1) will be identical to those for the 1 mg/kg (group 1, stage 1). After completion of the single dose infusion of 4 mg/kg (group 2, stage 1), the DSMB will assess the safety profile of the dose and provide a decision regarding the repeat dose studies (Stage 2).

Study Sites

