4.1 Inclusion Criteria (Stage 1 and Stage 2)

1. Willing and able to provide signed informed consent.
2. Age \geq 18 years
3. Diagnosis of moderate-to-severe OI based on history of more than 20 fractures in lifetime.
4. Glycine substitution in *COL1A1* or *COL1A2*, or pathogenic variants in *CRTAP*, *PPIB*, or *LEPRE1* (if genetic information is unavailable at screening, this may be assessed at screening visit on a clinical or research basis).
5. Females of child-bearing potential must have a negative urine pregnancy test, agree to and have the ability to use acceptable birth control method for entire duration of the study.
6. Males who enroll in the study and their partners must agree to use an acceptable form of birth control for the entire duration of the study.

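### Adverse events and serious adverse events are a primary safety component without regard to cause, but the statistical text summarizes only treatment-related events for that endpoint

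*Combined protocol and SAP*

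**What the plan says.** The Primary Outcome Measures in the synopsis list "Adverse events and serious adverse events" for Stage 1 and again for Stage 2. The primary objectives in Sections 4.7 and 4.8 do the same. The other safety components are vital signs, laboratory variables and EKG; Stage 1 also has pharmacokinetics as a primary outcome. None of these lists limits adverse events to those attributed to the drug.

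The Statistical Considerations, in the synopsis and in Section 6, contain one sentence on adverse events: "Treatment-Related Adverse Events will be summarized by dose groups". The next sentence says that vital signs, EKG, laboratory assessments, physical examinations and patient-reported symptoms will be described. The role of this set is then stated as "These will assess the primary endpoint of safety" in Section 6 and "These variables will assess the primary endpoint of safety" in the synopsis.

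Other sections cover all adverse events, but for monitoring. Under Section 5.1 the DSMB reviews the patterns and frequencies of all adverse events every six months, and the DMCC makes an aggregate report, broken down by severity and relationship to study drug among other things, available for site review. Under Section 5.5 the DMCC posts aggregate reports of all reported events for site investigators and IRBs, and the Safety Officer receives a table of non-serious expected events twice a year.

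**The concern.** The endpoint and its stated analysis cover different sets of events. The endpoint takes in every adverse event and every serious adverse event; the analysis takes in only those judged related. Read as written, a serious event called unrelated would not appear in the adverse event summary that is meant to assess the primary endpoint.

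This matters more here than in a controlled trial. Every group receives fresolimumab and there is no placebo or untreated arm, so whoever attributes an event has no concurrent rate to compare it with. With four participants planned per group, one event moved in or out by attribution changes a group's result visibly. In a related-only table, a participant with no event and a participant whose event was called unrelated look the same.

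**Working it through.** The plan gives no figure for this point, so the check sets the texts side by side.

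**1. Primary components affected.**
- Stage 1: pharmacokinetics, vital signs, laboratory variables, EKG, adverse events with serious adverse events = 5 components; 1 affected.
- Stage 2: vital signs, laboratory variables, EKG, adverse events with serious adverse events = 4 components; 1 affected.

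**2. Coverage of that component.**

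| Source | Events covered | Stated purpose |
|---|---|---|
| Synopsis outcomes; Sections 4.7 and 4.8 | All adverse events and serious adverse events | Primary safety outcome |
| Section 6; synopsis statistics | Treatment-related only | Assessment of the primary safety endpoint |
| Section 5.1, DSMB review | All | Monitoring |
| Section 5.1, DMCC aggregate report | Broken down by severity and relationship | Site review |
| Section 5.5, DMCC posted reports | All reported events | Sites and IRBs |
| Section 5.5, biannual table | Non-serious expected events | Safety Officer |

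Among the analyses tied to the endpoint there is 1 adverse event summary, limited to related events; 0 name all adverse events and 0 name serious adverse events.

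**3. Meaning of the term.** The statistical text does not define treatment-related. Section 5.3, under Immune Modulation, uses it causally, for events that the reporting physician considered to be so. Section 5.2 defines an adverse event as one associated with taking part in the study, which is wider than being caused by the drug. The two sets are therefore not the same by definition.

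**4. What the filter does to the protocol's own examples.** The same part of Section 5.3 gives two.
- Herpes zoster: 3 melanoma patients + 1 FSGS patient = 4 cases, of which 1 was considered related. A related-only table keeps 1 of 4 and drops 3. The protocol nevertheless counts all four, leaves open whether the drug raises the risk, and asks for careful monitoring.
- Vitiligo or hypopigmentation: 1 + 2 = 3 cases, all 3 considered related. The same table keeps 3 of 3.

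The filter thus does nothing for some events and removes most of others, depending on judgment.

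**5. Rules that do not depend on cause.** Section 5.7 allows the trial to be suspended or closed if two or more participants develop cancer, and Section 5.8 lists any cancer as a reason for discontinuation. Neither asks for relatedness. A cancer called unrelated could count under these rules and still be absent from the planned adverse event summary.

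**6. What cannot be calculated.** The documents give no expected incidence of adverse events in this population, so the number of events left out cannot be derived.

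**The case against.** The strongest reply is that all adverse events are in fact summarized. They are collected throughout, the DSMB sees all of them, and the DMCC reports can separate related from unrelated events. This stands, and it rules out the stronger statement that the trial plans no summary of all adverse events anywhere. It does not close the gap, because none of these outputs is described as the analysis of the primary endpoint.

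A second reply is that Section 6 never says only, and that treatment-related may be a slip for treatment-emergent. That is possible. If so, correcting the word would largely settle the matter for adverse events overall, although serious adverse events would still need to be named. The causal use of the term in Section 5.3 means that a slip cannot be assumed.

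A third is that physical examinations, laboratory shifts and patient-reported symptoms are described without a relatedness filter, so many events would surface there. This narrows the loss but does not replace counts of adverse events and serious adverse events. The statement in Section 5.8 that data acquired before termination enter the primary analysis concerns participants who discontinue; it adds no summary of all events.

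Two stronger inferences are tempting, and the documents do not support them. A reader might infer that participants would be less well protected or that escalation would rest on filtered data. But the decision to go to the higher single dose "will be determined by the DSMB based on adverse events, safety data collected, and discontinuation criteria", and no trial decision is tied to the related-only summary. A reader might also infer that fractures would be left out as part of the disease, since entry requires a "Diagnosis of moderate-to-severe OI based on history of more than 20 fractures in lifetime". No text excludes fractures from the adverse event summary; the exception for skeletal complications belongs to the discontinuation rules in Sections 5.7 and 5.8.

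**Conclusion.** The mismatch is real and should be corrected. One component of the primary safety outcome, 1 of 5 in Stage 1 and 1 of 4 in Stage 2, would be reported for the endpoint only through events called related. The statistical text names no summary of all adverse events or of serious adverse events for that purpose. The result would be an incomplete report of the primary safety finding, dependent on attribution without a concurrent comparator. It is not a failure of collection, monitoring or participant oversight.

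The conclusion rests on reading treatment-related in the causal sense that the protocol itself uses, and on taking the two statistical passages as the full statement of the endpoint analysis. Confidence in the textual mismatch is high. How many events it would hide is unknown; the one-in-four herpes zoster share comes from other patient populations and shows the mechanism, not the expected size.

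**What to change.** In Section 6 and in the synopsis, replace the sentence on treatment-related events with:

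> All adverse events and all serious adverse events will be summarized regardless of attribution, by stage and group (Stage 1: by dose; Stage 2: by infusion schedule), with treatment-related events shown as a subset.

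The groups need naming because the present grouping by dose does not describe Stage 2. For that stage, "The dose to be administered (1 or 4 mg/kg) will be chosen after completion of Stage 1", and its two groups differ in the number and timing of infusions.

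Add one counting rule. The synopsis says that "Participants enrolled in Stage 1 of this study may be enrolled in Stage 2 of the study if they meet eligibility", so for anyone in both stages an event should be counted in the stage in which it began or worsened.

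The cost is a few extra tables. The visit procedures and Section 4.10 already have adverse events documented at every visit from Day 1, and the DMCC report in Section 5.1 already breaks them down by relationship. No new data are needed, and no stopping or discontinuation rule changes.

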7.1 Registration

Registration of participants on this protocol will employ an interactive data system in which the clinical site will attest to the participant's eligibility as per protocol criteria and obtain appropriate informed consent. IRB approval for the protocol must be on file at the DMCC before accrual can occur from the clinical site.

The DMCC will use a system of coded identifiers to protect participant confidentiality and safety. Each participant enrolled will be assigned a local identifier by the enrollment site. This number can be a combination of the site identifier (location code) and a serial accession number. Only the registering site will have access to the linkage between this number and the personal identifier of the subject. When the participant is registered to participate in the study, using the DMCC provided web-based registration system, the system will assign a participant ID number. Thus each participant will have two codes: the local one that can be used by the registering site to obtain personal identifiers and a second code assigned by the DMCC. For all data transfers to the DMCC both numbers will be required to uniquely identify the subject. In this fashion, it is possible to protect against data keying errors, digit transposition or other mistakes when identifying a participant for data entry since the numbers should match to properly identify the participant.

7.2 Data Entry

Data collection for this study will be accomplished with online electronic case report forms. Using encrypted communication links, on-line forms will be developed that contain the requisite data fields.

